2.2.1 OUTCOME MEASURES

The primary outcome measure is the efficacy of liftiegrast ophthalmic solution 5% in treating the symptoms of dry eye in contact lens wearers as measured by change in total score on the CLDEQ-8 after 8 weeks of treatment.

Secondary and exploratory outcomes include:

- a. Change in tear osmolarity (measured via Tear Lab) at 8 weeks in the lifitegrast 5% group compared to the control
- b. Forced choice questionnaire at week 8 asking if the participant felt that their symptoms improved to the point that they would continue treatment outside of the study
- c. Change in total score on the CLDEQ-8 at 2 weeks and 4 weeks
- d. Trends in responses to individual questions

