5 STATISTICS

The clinical characteristics of subjects including demographics and lens modality will be first summarized using descriptive statistics in mean \pm SD for continuous variables or % (counts) for categorical variables, with attention to assessing balance in these characteristics by study arms, and with assessment of the distribution of variables, relevant to the choice of statistical tests. For the continuous outcomes, we will conduct the Kolmogorov-Smirnov or the Shapiro-Wilk test to confirm normality of measurements prior to performing statistical analyses. Detection of outliers will be done using histograms, box-plots, normal plots and summary statistics. Where appropriate, logarithmic transformation will be further done.

All analyses will be conducted using the principle of "intent-to-treat" in which every participant is assumed to have received his/her assigned intervention, regardless of adherence. In order to assess for the significant difference between study arms for the primary outcomes of change in total score on the CLDEQ-8 after 8 weeks of treatment or continuous secondary outcomes (change in tear osmolarity), bivariate comparisons will be first conducted using t-tests. Alternatively Wilcoxon nonparametric counterpart will be used for continuous variables that deviate from normality. The forced choice questionnaire will be compared as a percentage of "yes" responses between the two groups by a two-sample test of proportion. These univariate analyses will be followed by multivariable regression methods for an adjustment of all other potential confounding variables such as baseline clinical and demographic characteristics that differ by study arms.

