Alternatively, we will use longitudinal linear models to analyze the difference of changes in total score between study arms from the baseline to the follow-up times across baseline, 2nd, 4th and 8th weeks (i.e., mixed-effects regression models with a random subject effect and GEE with exchangeable and independent correlations). The models will be specified with random intercepts and slopes such that a linear trajectory representing outcome will be compared between groups. Group (arm)-specific (as well as individual-level) intercepts and slopes over the period of follow-up will be included as random effects, while other covariates will be modeled as fixed effects. All models will be adjusted for other clinical or demographic confounders. Residual-based diagnostics will be used to evaluate validity of model assumptions. Two sided p-values <0.05 will be considered to be statistically significant. All statistical procedures were performed using R statistical package (www.R-project.org).

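### The alternative longitudinal models fit a straight line and name no week-8 contrast, so in general they do not estimate the week-8 CLDEQ-8 change and cannot give separate week-2 and week-4 effects

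*Combined protocol and SAP*

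**What the plan says.** Section 2.2.1 defines the primary outcome as "change in total score on the CLDEQ-8 after 8 weeks of treatment". Item (c) of the secondary and exploratory outcomes is "Change in total score on the CLDEQ-8 at 2 weeks and 4 weeks".

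Section 5 starts with the week-8 change: "bivariate comparisons will be first conducted using t-tests", with a Wilcoxon test if normality fails and covariate-adjusted regression afterwards. It then adds a second route: "Alternatively, we will use longitudinal linear models to analyze the difference of changes in total score between study arms", covering the period "from the baseline to the follow-up times across baseline, 2nd, 4th and 8th weeks". The methods named are mixed-effects models and GEE.

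The form of time is then fixed: "The models will be specified with random intercepts and slopes such that a linear trajectory representing outcome will be compared between groups". On the arm terms the section says: "Group (arm)-specific (as well as individual-level) intercepts and slopes over the period of follow-up will be included as random effects".

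The section contains no term for visit as a category, no constraint or adjustment that equates the arms at baseline, and no contrast at week 8. Residual diagnostics are planned, but no fallback model is named for the case where the line does not fit.

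**The concern.** The outcomes are changes at specified visits. The longitudinal models compare straight lines. A slope difference times 8 weeks equals the week-8 difference only when the arm difference rises in a straight line from zero. Otherwise the fit spreads the misfit over slope and intercept, and because each arm has its own intercept, part of a real treatment effect can appear as a difference at week 0. Section 2.3 places randomization after the baseline assessments, so there is no treatment effect at week 0 to estimate.

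The line also fixes the modelled changes at weeks 2 and 4 at one quarter and one half of the modelled week-8 change, so it carries no separate information on outcome (c).

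At stake is a longitudinal result that may be reported beside, or in place of, the t-test while measuring something else. The plan does not say whether the slope difference or the fitted week-8 difference would be reported, and the two can err in opposite directions.

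**Working it through.** **Inputs.** Visits at weeks 0, 2, 4 and 8 (sections 2.4 and 5). Difference of 3 points, SDs of change 3.2 and 2.0, 15 per arm, two-sided 0.05 (section 3.3). The onset profile, within-person covariance and dropout are not given. I assume complete data at nominal times and vary the profile. The arm-specific terms are treated as freely estimated; any shrinkage from fitting them as random effects is not quantified.

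**The plan's own power.** Averaged variance of change = (3.2² + 2.0²)/2 = 7.12, so SD = 2.668 and d = 3/2.668 = 1.124. The noncentral t with 28 df and noncentrality 1.124 × √(15/2) gives 84.4%, matching Table 1. At d = 1 it gives 75.3%, as stated; at d = 1.2 it gives 88.7% against the stated 87.5%, which does not affect this point.

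**What the line returns.** Mean time = 3.5; centred times −3.5, −1.5, 0.5, 4.5; sum of squares 35. Let D be the true week-8 arm difference.

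Full effect from week 2, profile (0, D, D, D):
- slope = (−1.5 + 0.5 + 4.5)D/35 = 0.10D per week
- slope × 8 = 0.80D
- intercept difference = 0.75D − 0.10D × 3.5 = 0.40D
- fitted week-8 difference = 0.40D + 0.80D = 1.20D

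At D = 3 these are 2.4, 1.2 and 3.6 points. The slope-based changes at weeks 2 and 4 are 0.6 and 1.2 points, against a true 3 at both.

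Other profiles, same formulas:

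| Arm difference at weeks 0, 2, 4, 8 | Slope × 8 | Week-0 difference | Fitted week-8 difference |
|---|---|---|---|
| 0, D, D, D | 0.80D | 0.40D | 1.20D |
| Exponential, 2-week time constant | 0.91D | 0.23D | 1.14D |
| 0, D/2, D, D | 0.97D | 0.20D | 1.17D |
| Linear | 1.00D | 0 | 1.00D |
| 0, 0, D, D | 1.14D | 0 | 1.14D |
| 0, 0, 0, D | 1.03D | −0.20D | 0.83D |

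With complete, balanced data these values are the same under independence, exchangeable correlation, and random intercept plus slope. Choosing between the mixed model and either GEE therefore does not remove the bias.

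**Power of the slope test.** Assume equal, independent visit errors around each person's level. Error variance per visit = 7.12/2 = 3.56, and the SD of a person's slope × 8 = 8 × √(3.56/35) = 2.551.
- Full effect from week 2: 2.4/2.551 = 0.941, power 70%
- Exponential: 2.73/2.551 = 1.07, power 81%
- Half at week 2, full by week 4: 2.914/2.551 = 1.142, power 86%
- Linear: 3/2.551 = 1.176, power 87%

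The week-8 change has 84% in every case. When random slopes carry 0%, 50% or 80% of the change variance, simulation gives the slope test 67–70% for the week-2 plateau and 83–85% for the half-then-full profile.

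**A baseline-adjusted week-8 contrast.** With equal visit variances and baseline correlation ρ, residual variance = 7.12 × (1 + ρ)/2. At ρ = 0.3 the SD is 2.151, d = 1.39 and power 96%. At ρ = 0.7 the SD is 2.460, d = 1.22 and power 90% (27 df).

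**The case against.** The strongest reply is that the main comparison does not use these models. The t-test on week-8 change comes first, the adjusted regression also targets that change, and section 3.3 powers the trial on the t-test. This stands. A reader might infer that the primary result is biased; the documents do not support that unless the longitudinal result replaces the t-test. Which analysis decides is a separate question.

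A reader might also infer that the models understate the effect by 20%. That figure belongs to one contrast (slope × 8) under one assumed profile. The plan does not say that slope × 8 will be reported, and the fitted week-8 difference from the same lines is 20% too high. Nor is power generally lost with early onset: half the effect at week 2 and all by week 4 costs essentially nothing.

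It is tempting to add that selecting on a score of at least 12 at baseline produces an early fall that bends the trajectories. Such a fall is expected equally in both randomized arms, and with balanced data curvature common to both cancels from the slope difference. Only a nonlinear arm difference biases the contrast.

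Finally, the plan nowhere says that outcome (c) will be read from the line, and the opening sentence on the longitudinal models does speak of changes to the follow-up times. Both are true. But the specification that follows cannot deliver visit-specific changes, and section 5 does not expressly assign another analysis to weeks 2 and 4.

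**Conclusion.** The point holds in a limited, conditional form and is minor, because it concerns an alternative analysis. As specified, the longitudinal models do not in general estimate the week-8 change and cannot estimate the week-2 and week-4 changes separately. For an effect complete by week 2, a true 3 points reads as 2.4 or 3.6 depending on a contrast the plan does not name, with a false 1.2-point baseline difference and slope-test power of about 70% against 84%. For a half-then-full profile, slope × 8 is 3% low without power loss; for a linear arm difference there is no bias.

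These figures rest on assumed onset profiles, complete data and nominal visit times; the power figures also assume equal, independent visit errors. Moving all subjects to the extremes of the section 2.4 visit windows shifts slope × 8 for the week-2 plateau to between 0.63D and 0.99D.

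**What to change.** In section 5, replace the linear-trajectory specification with a repeated-measures model:
- visit (weeks 2, 4 and 8) as a categorical factor
- arm and arm-by-visit as fixed effects
- baseline score as a covariate, or a common baseline mean for both arms

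Name the week-8 arm contrast as the longitudinal result and report the week-2 and week-4 contrasts as outcome (c). The covariance structure and degrees-of-freedom method can be left to the trial statistician, but should be written down.

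Keeping the line and only equating the baselines is not a reliable repair: for the week-2 plateau it gives 1.33D under independence and 1.00D under exchangeable correlation of 0.5, so the answer depends on the working covariance.

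The cost is an edit to the plan and a few more parameters; no new data are needed. Some efficiency could be lost against the slope test if the arm difference is truly linear. Under equal visit errors no loss is shown: the baseline-adjusted contrast has about 90–96% power (baseline correlation 0.7 to 0.3), against 87% for the slope test in that case.

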3.3 SAMPLE SIZE JUSTIFICATION

Assuming normality, we calculated the statistical power for various detectable effect sizes using unpaired t-test in a two-sided hypothesis test with a significance level, 0.05, where the ratio of sample size of 1:1 is assumed between study arms. **Table 1** shows that our sample size will have adequate power to detect listed effect size. For example, we will achieve 84% power to detect a standardized mean difference of 1.12 between two groups of a size of 15 for each, which corresponds to a difference of score change by 3 with standard deviations 3.2 and 2.0 for each group⁵. Up to 40 subjects will be enrolled with the goal of randomizing 30 subjects (15 per arm). This will allow for a 25% screen-failure rate. Note that for each

domain score and the overall score, the power is the same for each effect size since they are standardized, but the mean change corresponding to a given effect size differs.

Table 1

Sample size (N)	Unpaired t-test		
N1 vs. n2	Effect size 1	Power (%)	
15 vs. 15	1	75.3	
	1.12	84.4	
	1.2	87.5	

¹ standardized mean difference of 2 groups

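### In the mixed-model option of the alternative longitudinal analysis, treatment arm is specified as a random effect, so the model as written gives a shrunken arm difference and no fixed lifitegrast-versus-vehicle contrast

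*Combined protocol and SAP*

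**What the plan says.** Section 5 (Statistics) compares the arms on week-8 change in CLDEQ-8 total score in stages. First, "bivariate comparisons will be first conducted using t-tests", with a Wilcoxon test if normality fails. Regression adjusted for baseline characteristics follows.

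The last paragraph then offers, as an alternative, "longitudinal linear models to analyze the difference of changes in total score between study arms". Two tools are named: "mixed-effects regression models with a random subject effect and GEE with exchangeable and independent correlations". The mixed model is described in two sentences. The first gives its aim: "The models will be specified with random intercepts and slopes such that a linear trajectory representing outcome will be compared between groups". The second gives its terms. On the random part it says: "Group (arm)-specific (as well as individual-level) intercepts and slopes over the period of follow-up will be included as random effects". On the fixed part it adds no more than this: "while other covariates will be modeled as fixed effects".

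The paragraph ends with a general rule: "Two sided p-values <0.05 will be considered to be statistically significant". No sentence in section 5 or elsewhere names arm, or arm by time, as a fixed effect in this model.

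**The concern.** A random effect suits a factor whose levels are a sample from a larger set and whose spread is of interest. Arm is the opposite case: there are two levels, both chosen by design, and the difference between them is the question.

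The sentence on model terms is hard to read any other way. Its parenthesis separates arm-level from individual-level terms and makes both random, and the word *other* before the covariates leaves arm outside the fixed part. Software given this specification estimates an arm variance from a single degree of freedom and then predicts each arm's deviation, shrunk toward the common mean. It prints no treatment coefficient with a standard error and CI.

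What is at stake is the usefulness of this one analysis. To report an ordinary arm difference from it, the statistician would have to depart from the written plan, possibly after seeing the data.

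**Working it through.** **Inputs.** From section 3.3: difference in change 3, SDs 3.2 and 2.0, 15 per arm, two-sided 5% level. From section 2.3: two arms. From section 5: visits at weeks 0, 2, 4 and 8. The documents give no variance components for the four-visit model, so those below are assumptions.

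**Step 1: reproduce the plan's power.** Section 3.3 states that "we will achieve 84% power to detect a standardized mean difference of 1.12 between two groups of a size of 15 for each"; its Table 1 gives 84.4%.
- Pooled SD = √((3.2² + 2.0²)/2) = √7.12 = 2.668, so the effect size is 3/2.668 = 1.124.
- Standard error of the difference = 2.668 × √(2/15) = 0.974.
- Noncentrality = 3/0.974 = 3.079, with 28 degrees of freedom.
- Noncentral-t power = 84.4%, which agrees with the plan.

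**Step 2: shrinkage with one random arm term.** Take the week-8 change score with arm random, two levels and n = 15 per arm. Let D be the observed difference, s the pooled SD and t the ordinary two-sample t.
- REML arm variance = max(0, D²/2 − s²/n).
- Predicted difference = D × max(0, 1 − 1/t²).

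| Observed D | t = D/0.974 | 1 − 1/t² | Predicted difference |
|---|---|---|---|
| 3 | 3.079 | 0.895 | 2.68 |
| 2 | 2.053 | 0.763 | 1.53 |
| 1 | 1.026 | 0.051 | 0.05 |

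With arm fixed, the estimates stay at 3, 2 and 1.

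**Step 3: the four-visit model as written.** Arm intercept and arm slope are now both random. The plan does not say whether they may correlate, and the answer depends on it. The true week-8 difference is 3 and the course is assumed linear.

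| Arm terms | Assumptions | Result | Shrinkage |
|---|---|---|---|
| Correlated (same formula, with the joint intercept–slope statistic T² in place of t²) | Week-8 change SD 2.668; baseline SD 2 or 4; slope share of change variance 0 or 50% | Mean prediction 2.71 to 2.86 | 1 − 2.86/3 = 4.7% to 1 − 2.71/3 = 9.7% |
| Independent | Direct REML fits | Ratio to unshrunk slope 0.883 to 0.893 | 10.7% to 11.7% |
| Independent | Subject intercept SD 3, slope SD 0.25 per week, residual SD 1.2 | 2.609 against 2.934 with arm fixed | 1 − 2.609/2.934 = 11.1% |

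The range is therefore roughly 5 to 12%. Smaller effects shrink by more: under the last set of assumptions with a true difference of 1.5, the model gives 1.245 against 1.685, which is 26%. The amount depends on the assumed variances; the direction does not.

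**The case against.** **Ordinary intent.** The same paragraph speaks of a random subject effect and says the trajectories are to be compared between groups. Both fit a conventional model with arm fixed and participants random. This stands as a likely explanation, but not as a correction: the phrase about the subject effect does not make arm fixed, and the more detailed sentence after it makes arm random.

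**Only an alternative analysis is touched.** This stands in full. The t-test, Wilcoxon test, adjusted regression and sample size do not use the model. GEE has no random effects and can carry arm as a coefficient, although its mean model is not spelled out.

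**A reader might infer that the significance rule has nothing to act on.** That goes too far. The 0.05 rule also serves the other analyses in section 5, and a test of the arm variance would give the mixed model a p-value. What is missing is a fixed coefficient with a CI.

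**A reader might infer that the remaining variance test is weaker.** The documents do not support this. In the one-term case the likelihood-ratio statistic is 29 ln((28 + F)/29) − ln F, with F = t². Its derivative, 28(F − 1)/(F(28 + F)), is positive for F > 1, so the statistic rises with |t|. At a true 5% size the cutoff is about 1.60, which means |t| > 2.048. That is the t-test's own rejection region, with the same 84.4% power. The asymptotic cutoffs 2.706 and 3.841 give 74% and 64% power only because their true sizes are 2.3% and 1.1%, and the plan prescribes neither.

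**A reader might also fault the straight line.** That is a legitimate modelling choice, and any bias depends on a time course the documents do not give. For an invented course of 0, 3, 3, 3, eight times the fitted slope is 2.40, yet the same line's fitted week-8 difference is 1.20 + 2.40 = 3.60. No general conclusion follows.

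**Conclusion.** The point holds as a specification error in one option of an alternative analysis. As written, the mixed model does not deliver the contrast it was introduced to provide. The one-term shrinkage figures follow from the section 3.3 inputs. The four-visit range rests on assumed variances, an assumed linear course and an unstated choice about correlation between the arm terms.

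It should not be read as a threat to the primary comparison, as a loss of power, or as grounds for replacing the linear trajectory. Severity: minor.

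**What to change.** Replace the sentence on model terms in the last paragraph of section 5 with:

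*Arm, time and arm-by-time will be fixed effects, with other covariates also fixed; random intercepts and slopes will be at participant level only; the arm difference in change at week 8 will be reported with its 95% CI.*

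Whether time enters as linear or categorical can stay with the statistician.

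The cost is a wording amendment, which needs IRB review and approval under the Statement of Compliance. It requires no new data and no extra participants, and leaves the sample size as it is.
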